
Ginseng appears to be nontoxic, both in the short and long term, according to the results of studies in mice, rats, chickens, and dwarf pigs [120-124].

In summary, there are limited studies that used Panax ginseng for cancer related fatigue. the abstract of the results of a randomized study on cancer related fatigue in ASCO Proceeding 2008 shows it is well tolerated with activity against cancer related fatigue. However dose has not been mentioned. In prior trials in non-cancer patients, e.g for sexual dysfunction (see table 1) higher doses have been more effective. The common side effects at various doses have been used and generally well-tolerated, and its adverse effects are mild and reversible. The efficacy is more at higher doses as also shown in study by Barton etal 2009 Journal of Supportive care in cancer. A recent studies(125-127) shows some of the side effects reported include nervousness, insomnia, headache, skin eruptions, stomach upset, and increased menstrual bleeding and breast tenderness has been reported with the use of Panax ginseng. In our controlled clinical trial at MDACC we plan to closely monitor the effects of drug and placebo as outlined in the IRB protocol. We have also added the Dose Continuation, Modification and Interruption and trial stopping parameters.

B.9. Significance: Fatigue is a frequently debilitating symptom of cancer, as well as a common side effect of cancer treatment. At present, there are limited treatment options for the management of cancer-related fatigue (CRF). In clinical practice, more than 83% of patients use complementary and alternative medicines for treatment of cancer or symptoms. Ginseng is widely used in the United States as a

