Patients will be randomly assigned to one of the two treatment arms. The randomization schema will be based on parameters input into RANLST, a randomization program developed at UTMD Anderson and supported by an NCI grant.

C.6. Clinical Trial Design and Treatment Plan:

This study will have (1) Phase I: an initial non dose escalating phase to evaluate dose limiting toxicity. A total 30 evaluable patients will be enrolled in this phase. After study completion of the 30 evaluable patients (2) Phase II a second phase- RCT double blind phase will be started and (3) Both phases will have an open labeled phase. Patients in both Phase I or II may continue the ginseng in the open labeled extension phase if there are no grade 2 or more toxicity as per CTRC criteria as determined by the PI. A

total of 158 eligible patients will be enrolled in both phases of the trial (30 evaluable in phase I + 128 in phase II). (See Study Design Fig. 6).

Evaluable patients will be defined as any patient enrolled on the study that has taken at least one dose of treatment (i.e., either ginseng or placebo), making them available for toxicity and response.

C.6.1. Double-Blind Phase Dosing Patients will be randomized to one of two experimental groups receiving the treatments detailed below.

- The placebo group (**Arm 1**), will receive oral placebo twice daily for 29 days.
- The Panax ginseng group (Arm 2) will receive ginseng capsules 400 mg twice daily for 29 days.

Unblinding Procedure:

- 1. The Statistician and the investigational pharmacist will have access to the codes/assignments.
- 2. The codes will be revealed only If there is a safety issue and the treating physician needs to be aware of the treatment assignment.
- 3. The PI should be contacted regarding and give approval for un-blinding
- 4. The Investigator/research team must inform the IND Office when un-blinding occurs.

C.6.2. Open-Label extension Phase

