 Serious adverse events will be forwarded to FDA by the IND Sponsor (Safety Project Manager IND Office) according to 21 CFR 312.32.

It is the responsibility of the PI and the research team to ensure serious adverse events are reported according to the Code of Federal Regulations, Good Clinical Practices, the protocol guidelines, the sponsor's guidelines, and Institutional Review Board policy.

Adverse events will be captured according to the recommended AE recording guidelines for a Phase II protocol.

	Recommended Adverse Event Recording Guidelines								
Attribution	Grade 1	Grade 2	Grade 3	Grade 4	Grade 5				
Aunouton									
Unrelated	Phase I	Phase I Phase I Phase I Phase I Phase I		Phase I Phase II Phase III	Phase I Phase II Phase III				
Unlikely	Phase I	Phase I Phase I Phase I Phase II		Phase I Phase II Phase III	Phase I Phase II Phase III				
Possible	Phase I Phase II	Phase I Phase II Phase III	Phase I Phase II Phase III	Phase I Phase II Phase III	Phase I Phase II Phase III				
Probable	Phase I Phase II	Phase I Phase II Phase III	Phase I Phase II Phase III	Phase I Phase II Phase III	Phase I Phase II Phase III				
Definitive	Phase I Phase II	Phase I Phase II Phase III	Phase I Phase II Phase III	Phase I Phase II Phase III	Phase I Phase II Phase III				

Optional Procedures (Blood Draws): Serum and peripheral blood lymphocytes will be an optional procedure for all eligible patients. If the patient provides consent for the optional blood draw and serum is collected, the serum will be stored. On completion of the study, a future study will look at the change in levels of serum cytokines (IL-1 β , IL-6, IL-10, and TNF- α) and cytokines in the induced monocytes (IL-1 β , IL-6, IL-10, and TNF- α) to see if there is a correlation with the proportion of patients with decreased fatigue and with those who have no decrease in fatigue. *Methods:* Plasma will be harvested from blood specimens and stored frozen at -80°C for cytokine batch analyses at a later date. The assays that would be performed in the future would require as little as 50 µL of serum or plasma. Serum cytokines levels of IL-1 β , IL-6, IL-10, and TNF- α would be analyzed in a future study for samples collected at baseline, Day 15 and 29.

C.9. Statistical Analysis

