This is a preliminary study to explore the efficacy of P. ginseng in reducing fatigue as measured by the Functional Assessment of Cancer Therapy- Fatigue (FACIT-F) subscale. Because this Panax ginseng has not been previously evaluated in cancer related fatigue, we will implement this study in two phases. In the first phase(initial non dose escalating phase), we will enroll up to 30 patients in the Arm 2 (treatment arm); patients will not be enrolled in the placebo arm. Recruitment will be halted until these original 30 patients can be evaluated for DLTs. In the second, main phase patients will be randomized to receive either Panax ginseng or placebo. As a

2009-0854 January 21, 2016 Page 23 of 33

primary analysis, we will assess the level of fatigue at baseline and after 29 days to determine group differences in fatigue changes over time using analysis of variance. This analysis will test for differences between groups, differences over time, and a group by time interaction. We will also perform a repeated measures analysis by group using all available time points (for the FACIT-F fatigue subscale at baseline, day 15 and day 29). This analysis will test for differences between groups, differences over time, a group by time interaction, and trends over time. For all analyses of continuous variables, if the data are not approximately normally distributed, we will either use a nonparametric equivalent of the statistical test or we will transform the variable to achieve approximate normality. The design of the study is intent to treat, i.e., it is our aim to analyze anyone who received at least a single dose for both toxicity and response. Response would be considered clinical beneficial if they improve 3.5 points on the FACIT- F fatigue subscale at day 29 or day 15 (if day 29 is unavailable). Patient who have not completed at least day 15 would be considered inevaluable for consideration of clinical benefit.

Pilot Analysis:

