We will summarize patient characteristics of all patients enrolled in the pilot study. Means and standard deviation or medians and IQRs will be calculated. We will also perform exploratory analyses on the changes in FACIT-F subscale (primary outcome measure) from baseline to Day 29 and baseline to Day 57. Similar analysis will be conducted for the secondary outcomes (FACT-G, ESAS symptoms, HADS, SDMT, six- minute walk test, Borg Scale, GSE and Hand Grip Strength and Endurance Test). Based on whether the data is normally distributed (Shapiro-Wilk test) we will use paired t-tests or Wilcoxon Ranked Sum tests. We will also summarize fatigue scores, other secondary outcomes at each point in time and the frequency and type of side effects as determined by NCI CTCAE V4 criteria.

Safety Monitoring

Safety Monitoring

Because this Panax ginseng has not been previously evaluated in cancer related fatigue, we will implement this study in two phases and we will utilize early stopping rules for dose-limiting toxicities (DLTs) for 30 patients in the treatment arm (Arm 2, Panax ginseng 800mg/day) before the main phase of the study begins. A DLT is defined as any Grade 3 or 4 toxicity that is attributable to the treatment regimen.

In the first phase, we will enroll up to 30 evaluable patients in the Arm 2 (treatment arm); patients will not be enrolled in the placebo arm. Recruitment for the main study will be delayed until these original 30 patients are evaluated for DLTs. We will base early stopping rules on a method proposed by Thall et al., (160) and using the Multc99 software from the Department of Biostatistics.

To ensure that the true DLT rate is sufficiently low, we will terminate the study early if the probability that the estimated toxicity rate is greater than 10% (given the results) is greater than 0.95. We assume a prior of Beta (0.1,0.9) in these calculations. The study will be stopped early if (# patients with DLT) / (# patients evaluated) >= 3/6, 4/10, 5/16, 6/22, or 7/29.

The table below shows operating characteristics given differing true toxicity rates based on 10000 simulations for each row:

	Probability	Achieved Sample Size		
True DLT rate	Early Stopping	25 th , 50 th , 75 th percentiles		
1%	<0.0001	30	30	30

Operating Characteristics for first phase early stopping rule (based on DLT)

3%	0.002	30	30	30
5%	0.013	30	30	30
8%	0.053	30	30	30
10%	0.116	30	30	30
15%	0.324	20	30	30
20%	0.597	9	21	30
25%	0.791	8	14	27
30%	0.917	6	9	17
40%	0.993	6	7	9

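### The 30-patient Phase I toxicity stage is put under the Phase II adverse-event recording rule, so Grade 1 events judged unrelated or unlikely are left out of its side-effect summary

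*Combined protocol and SAP*

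**What the plan says.** **Recording rule.** The same sentence appears below Table 3 (Study Assessments) and in C.8, just above the recording table: "Adverse events will be captured according to the recommended AE recording guidelines for a Phase II protocol". Neither place separates the two stages of the trial.

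**First stage.** C.1 and C.6 call it "Phase I: an initial non dose escalating phase to evaluate dose limiting toxicity". It takes 30 evaluable patients, all on ginseng. C.9 confirms that "patients will not be enrolled in the placebo arm". B.4.2 gives closer safety monitoring as the reason for having two phases.

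**Recording table (C.8).** Each cell names the protocol phases for which an event of that grade and attribution is recorded. The Unrelated and Unlikely rows list Phase I alone at Grade 1. The Possible row begins "Possible Phase I Phase II Phase I Phase II Phase III", and the Probable and Definitive rows read the same, so Phase II protocols record such events at every grade.

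**What is to be reported.** Objective A.2 includes side effects and tolerability. For the first stage, the Pilot Analysis in C.9 will summarise "the frequency and type of side effects as determined by NCI CTCAE V4 criteria", with no restriction by attribution.

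**Where events are entered.** C.6.2 makes the PDMS/CORe database both the source document and the case report form for adverse events. The Toxicity Evaluation paragraph in C.7.2.1 says that events go into the medical record and into PDMS/CORe. Neither mentions a filter.

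**The concern.** Under the Phase II column, whether a Grade 1 event enters the data depends on someone's opinion of its cause. That is an ordinary economy in many Phase II trials. It fits poorly with a single-arm stage that the protocol itself calls Phase I and runs to learn about toxicity.

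Two features sharpen the point. First, B.7 expects ginseng's adverse effects to be mild and reversible, and its closing summary says that "some of the side effects reported include nervousness, insomnia, headache, skin eruptions, stomach upset, and increased menstrual bleeding and breast tenderness". Grade 1 is therefore where much of the signal may lie. Second, the patients have cancer and may be on chemotherapy or radiotherapy (inclusion criterion 11), so another explanation for a mild symptom is often at hand. In the first stage no placebo group can show later whether those attributions were right.

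At stake is the completeness of one planned summary, and whether a reader can tell what it covers. An event never entered cannot be reliably recovered afterwards.

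**Working it through.** This is a question of which rule applies, so most of the check sets the sections side by side.

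**1. Which events the rule drops in the first stage.**

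| Event | Phase I column | Phase II column (the one applied) |
|---|---|---|
| Grade 1, Unrelated or Unlikely | recorded | not recorded |
| Grade 2-3, Unrelated or Unlikely | recorded | not readable in the text available here |
| Any grade, Possible, Probable or Definitive | recorded | recorded |
| Grade 4-5, any attribution | recorded | recorded |

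The Grade 2-3 cells of the first two rows are run together in the extracted text; one row reads "Unlikely Phase I Phase I Phase I Phase I Phase II" before the later cells. Only Grade 1 is clear, so the finding stops there.

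**2. How much observation is involved.** Table 3 schedules toxicity evaluation on Days 8, 15, 21, 29, 36, 43 and 57, which is 7 post-baseline contacts. For 30 patients that is at most 30 × 7 = 210 evaluations: 30 × 4 = 120 up to Day 29 and 30 × 3 = 90 in the open-label extension. The documents give no expected number of Grade 1 events or split by attribution, so the number omitted cannot be estimated.

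**3. Whether the stopping rule is affected.** The plan's own figures come first. C.9 stops the stage if the posterior probability that the toxicity rate exceeds 10% is above 0.95, with a Beta(0.1, 0.9) prior. With x events in n patients the posterior is Beta(0.1 + x, 0.9 + n − x). Checking after every patient from n = 6 gives boundaries that change at 3/6, 4/10, 5/16, 6/22 and 7/29, exactly as stated. Exact early-stopping probabilities compare with the simulated ones as follows:

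| True DLT rate | Stated | Recomputed |
|---|---|---|
| 5% | 0.013 | 0.013 |
| 10% | 0.116 | 0.112 |
| 15% | 0.324 | 0.332 |
| 20% | 0.597 | 0.592 |
| 30% | 0.917 | 0.919 |

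A dose-limiting toxicity is an attributable Grade 3 or 4 event. Taking attributable to mean Possible or stronger, both columns record all such events. The choice of column therefore leaves these probabilities unchanged.

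**4. Whether the randomised comparison of mild events loses power.** Assume, for illustration only, a mild event with a 10% background rate in both arms and a further 20% caused by ginseng. Use 64 patients per arm and a two-sided chi-square test at |z| > 1.96, enumerated exactly. Let b and d be the fractions of background and drug-caused events that are filtered out. Recorded rates are 0.10(1 − b) on placebo and 0.10(1 − b) + 0.20(1 − d) on ginseng.

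| b | d | Placebo | Ginseng | Power |
|---|---|---|---|---|
| 0 | 0 | 10% | 30% | 0.825 |
| 40% | 40% | 6% | 18% | 0.565 |
| 60% | 60% | 4% | 12% | 0.395 |
| 60% | 30% | 4% | 18% | 0.757 |
| 60% | 20% | 4% | 20% | 0.838 |
| 60% | 10% | 4% | 22% | 0.897 |

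Equal filtering costs power. Filtering that removes mainly background events can leave power unchanged or raise it. The documents do not say which would occur.

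**The case against.** The strongest reply is that the stage is meant to evaluate dose-limiting toxicity, and that this purpose is fully served. Attributable Grade 3-4 events are captured, Grade 4-5 events are captured whatever the attribution, and C.8 requires serious adverse events to be reported regardless of attribution. This stands.

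Second, the omitted events are not wholly lost. The medical record may hold them, and the ESAS is collected at baseline and at all seven later contacts whatever the attribution. This stands in part. The ESAS covers sleep, nausea and anxiety among its ten items, but has none for headache, skin eruptions, dizziness, bleeding or breast tenderness. The medical record is not named as the source for the planned summary.

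Third, the protocol names the expected effects in B.7 and in its dose-modification table, so an alert investigator may rate them Possible, and they would then be recorded. That is plausible and limits the damage, but it does not remove the mismatch between rule and stage.

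Fourth, no planned test depends on Grade 1 events. The interim comparison in C.9 concerns events above Grade 2, and other toxicity is only summarised. This also stands.

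A reader might infer more: that Grade 2 events are dropped too, that the whole tolerability objective rests on attribution, or that the randomised comparison of mild events loses power. The documents support none of these. The Grade 2 cells cannot be read here, severe and serious events do not depend on the filter as shown above, and the direction of any power effect turns on an assumption the documents do not settle.

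**Conclusion.** The inconsistency is real and narrow. As written, Grade 1 events rated Unrelated or Unlikely in the first 30 patients would be missing from the adverse-event data set. The planned first-stage summary implies no such exclusion, and two other sections describe entry without one. The conclusion rests on the legible Grade 1 cells and on reading the repeated sentence as covering the whole trial, since no exception is given. How many events are affected is unknown. No stated operating characteristic changes, and no power loss in the randomised phase is established. Severity is minor, because tolerability is an exploratory objective and the safety safeguards are intact.

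**What to change.** - Below Table 3 and in C.8, state that the table's Phase I column applies to the first 30 patients, including their open-label extension, and the Phase II column to the randomised phase.
- Reconcile C.6.2 and the Toxicity Evaluation paragraph in C.7.2.1 with that statement, so that all four places give one rule for what enters PDMS/CORe.
- For the randomised phase, do one of two things. Either label the tolerability summaries as excluding Grade 1 events judged unrelated or unlikely, or, optionally, record the expected effects named in B.7 and in the dose-modification table at every grade whatever the attribution. Under the second option, keep attribution as a separate field and tabulate by arm.

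The cost is more data-entry lines for 30 patients, and for the named terms in the randomised phase if that option is taken. Toxicity is already evaluated at every post-baseline contact, so no visit or test is added and no treatment rule changes.

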Specific aim# 1. To explore effects of 800mg of P. ginseng as compared to placebo on cancerrelated fatigue as determined by FACIT-F at the end of 29 days. We hypothesize that patients randomized to receive P. ginseng will demonstrate greater improvement in CRF than Placebo. To prove this hypothesis we will measure the intensity of fatigue using the following instruments: FACIT-F (145) Although two measures used to assess fatigue were the (1) FACIT-F and (2) ESAS, the primary end point was the FACIT-F score. The FACIT-F is a well-validated quality-of-life instrument widely used for the multidimensional assessment of cancer-related fatigue in clinical trials. (147) It consists of 27 general quality-of-life questions divided into four domains (physical, social, emotional, and functional), plus a 13-item fatigue subscore. This 13-item fatigue subscore was the primary outcome of our study. The patient rates the intensity of fatigue and its related symptoms on a scale of 0 to 4. The total score ranged between 0 and 52, with higher scores denoting less fatigue. In a recent metanalysis of pharmacological treatments of cancer related fatigue (146) of 27 eligible treatments trials that were selected, FACIT-F was used a primary end point in majority of them. It has been also been used in prior fatigue treatment studies by our team. We have currently have 3 (NIH) R01 projects in our team using FACIT-F tool and we have a large database with FACIT-F tool. Our research team is very familiar using FACIT-F tool and this will allow us to compare results with those of other interventions in our database (such as Methylphenidate, Nursing Telephone intervention for treatment of fatique). Test-retest reliability coefficients for the fatique subscale are 0.84-0.90. This scale has also demonstrated strong internal consistency (α =0.93-0.95).

Specific aim# A.2

- To explore its effect on physical activity as measured by six minute walk test.
- To explore its impact on quality of life-related variables: mood (HADS), and quality of life domains (FACT-G)) in these patients.
- To explore its side effects and tolerability of *P. ginseng* in these patients.
- To estimate the proportion of patients experiencing clinical benefit in each arm and to compare these proportions between arms

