During the second phase of the study, the DSMB will meet to assess toxicity in an unblinded fashion at defined intervals (annual review) and will terminate the study if the incidence of DLT on either arm is judged by the DSMB to be excessive.

Power Considerations: There are no randomized controlled trials on P.ginseng for the management of CRF. The only intervention with Level I evidence for effectiveness in CRF is exercise. Among the most important clinical trials conducted on the intervention are those of Segal etal [154-156]. They have determined the clinically important difference in fatigue as a result of intervention as compared to placebo. Since these two studies used FACIT-F (our primary outcome) we have used these studies for power/sample size calculation. We postulate that if P.ginseng is an effective intervention we will observe a difference in response at Day 29(primary end point) similar and higher to those observed in the Exercise studies. We plan to include 50 evaluable patients per group. If we assume that our dropout rate will be no higher than 20%, we will recruit 64 patients into each group, for a total of 128 patients. As we could find no other published studies about the use of Panax ginseng in cancer patients, we base our sample size estimate on previous research in resistance exercise training [154]. This study found that the difference between groups in changes in the FACIT F subscale at 24 weeks was 4.78, significant at p=0.002, and was powered to detect a difference of 3.5 points based on a similar study in exercise resistance [155] that found standard deviations in difference scores over 12 weeks of 5.8. Studies such as Cella et al, 2002[156], state that differences of 3-5 points or more on the FACIT-F subscale are clinically important differences. If we assume a standard deviation of 5.8 in difference scores, with 50 evaluable patients per group we will be able to detect differences as small as 3.3 or larger with a twosided significance level of 0.05 and 80% power. With standard deviations in difference scores as large as 8.8, we will still be able to detect differences of 5 points or greater.

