Evaluable patients will be defined as any patient enrolled on the study that has taken at least one dose of treatment (i.e., either ginseng or placebo), making them available for toxicity and response. Although we expect dropouts (20% of 128 patients) the primary analysis will not include dropouts, but a secondary analysis would carry forward the last known FACIT-F score for those patients who had received at least one dose.

Yearly interim analyses will be conducted by the biostatistician and the results will be presented to the MDACC DSMB office. Results will be presented overall and by arm retaining the blinding as to arm assignment unless requested to reveal arm assignment by the DSMB (usually only made if one or both of the arms show a significantly less than expected efficacy or toxicity). In that case the statistician will reveal the arm assignments to the DSMB. The PI and other collaborators (other than the statistical collaborator) will remain blinded as to the arm assignments of patients.

As a part of each interim analysis, we will determine if either arm has significantly more occurrences of greater than grade 2 adverse events (p<0.05) as compared to each other. If this is found it will be reported to the DSMB and the study may be terminated early.

A formal interim analysis will be conducted when a total of 50 evaluable patients (one-half of the total number of evaluable patients) have been evaluated for 29 days. This interim analysis will allow for the early termination of the study in light of evidence that patients in either arm improve significantly than the other arm (early stopping due to superiority) or that patients in the two arms have similar improvement (early stopping due to futility). In order to provide for an overall two-sided significance level of approximately 0.05 for the study, the interim analysis will have a Lan-DeMets monitoring boundary with an O'Brien-Fleming stopping rule for both tests (EaSt, version 5, Cytel Software Corporation). The decision boundaries for the interim test will be to accept the null hypothesis of no treatment difference (futility) if the test statistic |Z| < 0.348 (p > 0.73), reject the null hypothesis if |Z| > 2.96 (p < 0.003), or otherwise continue the trial. The final test cut-off will be to reject the null hypothesis if |Z| > 1.95 (p < 0.051).

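### The primary change-score test is implied but not named as the sole test, and it ignores baseline FACIT-F as a covariate; a baseline-adjusted Day-29 contrast is a nearly free, modest gain

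*Combined protocol and SAP*

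**What the plan says.** Section C.9 (Statistical Analysis) compares fatigue at baseline and after 29 days "to determine group differences in fatigue changes over time using analysis of variance". It then lists the output: "This analysis will test for differences between groups, differences over time, and a group by time interaction". A second, repeated-measures analysis adds Day 15 and reports the same three tests plus trends.

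Four places show which effect is meant:

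- the purpose clause just quoted;
- Specific aim 1 in C.7.2.1: "We hypothesize that patients randomized to receive P. ginseng will demonstrate greater improvement in CRF than Placebo";
- Power Considerations, which sizes the trial on change: "If we assume a standard deviation of 5.8 in difference scores, with 50 evaluable patients per group";
- the formal interim analysis, which allows stopping when "patients in the two arms have similar improvement (early stopping due to futility").

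The interim and final boundaries are set on |Z| (2.96 and 0.348 at the interim, 1.95 at the end). The futility rule is to "accept the null hypothesis of no treatment difference (futility) if the test statistic" falls below its limit. The effect that yields Z is not named.

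No section makes baseline FACIT-F a covariate. B.1 says that situational factors will enter all analyses, but it does not name baseline FACIT-F, and C.9 does not take the statement up. C.5 says only "The randomization schema will be based on parameters input into RANLST", without listing the parameters.

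**The concern.** Two things are missing.

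**The deciding test.** Three effects are listed under the primary analysis and one set of |Z| boundaries follows. The intent can be inferred, but a rule that can stop the trial early should rest on a named statistic. The group main effect averages in a score taken before treatment, so it is a different and much weaker test than the one the trial is sized for.

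**The baseline covariate.** With two time points, the group-by-time interaction is the two-sample t-test on Day 29 minus baseline. That fixes the slope of Day 29 on baseline at 1. Analysis of covariance (ANCOVA) estimates the slope instead. Both estimate the same treatment effect under randomisation, and ANCOVA has the smaller variance unless the true slope is 1. It also removes the part of a chance baseline difference that the change score leaves in. Balance on baseline FACIT-F cannot be assumed, because the randomisation parameters are not listed.

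Precision and clarity are at stake, not validity.

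**Working it through.** **Inputs from the plan (C.9, Power Considerations).** Difference 3.3 points, SD of change 5.8, 50 evaluable per arm, two-sided 0.05, 80% power. Second case: difference 5, SD of change 8.8.

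**Inputs assumed.** The documents give neither the baseline-to-Day-29 correlation r nor the raw SDs. C.7.2.1 offers only a reliability figure: "Test-retest reliability coefficients for the fatique subscale are 0.84-0.90". I use r = 0.5, 0.6 and 0.7, and also 0.84 and 0.90 from that range. Let k = SD at Day 29 / SD at baseline. I use k = 1, 1.15 and 1.3, because the entry rule of fatigue 4 or more out of 10 may narrow the baseline spread.

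**Step 1. Reproduce the plan.** The standard error is 5.8 × √(2/50) = 1.16, so the noncentrality is 3.3/1.16 = 2.84. The noncentral t with 98 df gives 80.4% power and a detectable difference of 3.28. For SD 8.8 the power at 5 points is 80.3% and the detectable difference 4.98. Both match the stated 3.3 and 5, so the sizing belongs to the change-score test.

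**Step 2. Variance under adjustment.** Hold the SD of change at 5.8.

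- Baseline SD: s0 = 5.8 / √(1 + k² − 2rk)
- ANCOVA residual SD: k × s0 × √(1 − r²)
- Saving in variance: s0²(1 + k² − 2rk) − k²s0²(1 − r²) = s0²(1 − rk)², which is never negative

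Example, k = 1 and r = 0.5: s0 = 5.8/√1 = 5.8; residual SD = 5.8 × √0.75 = 5.02; the variance falls by 25%.

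**Step 3. Power at 3.3 points** (97 df; detectable difference in brackets). The change-score reference is 80.4% (3.28).

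| r | k = 1 | k = 1.15 | k = 1.3 |
|---|---|---|---|
| 0.5 | 90.2% (2.84) | 86.5% (3.02) | 83.9% (3.13) |
| 0.6 | 88.3% (2.94) | 84.4% (3.11) | 82.1% (3.21) |
| 0.7 | 86.3% (3.03) | 82.5% (3.19) | 80.8% (3.27) |
| 0.84 | 83.6% (3.15) | 80.5% (3.28) | 81.1% (3.25) |
| 0.90 | 82.4% (3.20) | 80.6% (3.27) | 83.7% (3.14) |

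The gain is smallest where rk is near 1 (for example 1.15 × 0.84 = 0.97).

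**Step 4. Simulation with the exact ANCOVA standard error** (20,000 trials per case, Monte Carlo SE about 0.3 points), change score against ANCOVA:

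- k = 1, r = 0.5: 80.5% v 89.6%
- k = 1, r = 0.9: 80.2% v 81.7%
- k = 1.3, r = 0.7: 80.0% v 80.1%
- k = 1.15, r = 0.84 (worst case): 80.4% v 80.1%

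**Step 5. Chance imbalance.** A one-SE baseline difference is s0 × √(2/50). It shifts the change-score estimate by (1 − rk) times that amount. At r = 0.6:

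- k = 1: imbalance 1.30 points, shift 0.4 × 1.30 = 0.52
- k = 1.15: imbalance 1.19, shift 0.31 × 1.19 = 0.37
- k = 1.3: imbalance 1.09, shift 0.22 × 1.09 = 0.24

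**Step 6. Why the name matters.** Take k = 1. The group main effect compares means of baseline and Day 29, so the 3.3-point effect becomes 1.65. The SD of that mean is s0 × √((1 + r)/2): 5.02 at r = 0.5 and 6.90 at r = 0.7. Power by the t-test is about 37% and 22%. If success could be claimed on either this test or the interaction, type I error would be 1 − 0.95² = 9.75% (simulated 9.4% to 9.7%). Nothing in the plan says that this is intended.

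**The case against.** The strongest reply is that this is a preference, not a defect. A change score is a legitimate choice in a study that calls itself preliminary, the sizing agrees with it, and the test is valid. That stands, and it limits the point to an improvement.

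Second, the gain depends on quantities that the plan does not give. Gains of 2 to 10 points need equal SDs, yet the entry rule gives a reason to doubt equal SDs. At k = 1.3 and r = 0.5 to 0.7 the gain is 0.4 to 3.5 points. At the reliability figures with k = 1.15 it is 0.1 to 0.2. This also stands: the fair statement is about 0 to 10 points. It does not turn the change into a risk, because the worst simulated loss, 0.3 points, is about one Monte Carlo SE.

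Third, chance imbalance is already part of the change score's standard error, so Step 5 shows the mechanism of Step 3 and is not a second benefit. That is correct.

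Fourth, four places already show which contrast is meant, and a reader must ignore all of them to take a main effect as decisive. That is largely right. Naming the contrast supplies missing detail and resolves no contradiction. The |Z| statistic is still unnamed, and one sentence settles it.

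**Conclusion.** The point holds. The primary contrast is implied but not named as the sole test, and it is not adjusted for baseline FACIT-F. The planned change-score test is valid, unbiased over randomisation and meets its stated power.

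Against 80.4%, adjustment gives 82.4% to 90.2% power with equal SDs and r from 0.90 down to 0.5, and a detectable difference of 2.84 to 3.20 points instead of 3.28. With a larger Day-29 SD the gain lies between about zero and 6 points. These sizes rest on assumed r and k, on the SD of change held at 5.8, and on a single-look 5% test that ignores the interim boundaries. That the variance is never larger, apart from one degree of freedom, does not depend on r or k.

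The change should be made, but the trial is not unsound without it.

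**What to change.** In C.9:

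1. State as the sole primary test the difference between arms in the Day-29 FACIT-F fatigue subscale from an ANCOVA with baseline FACIT-F as covariate, or the same contrast from a baseline-adjusted mixed model.
2. Apply the interim and final |Z| boundaries to that contrast only.
3. Label the group and time main effects of the analysis of variance as descriptive.

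A side point, not quantified here: keep this test fixed whatever the distribution of the data, with a rank-based version as a sensitivity analysis.

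The cost is SAP wording and one degree of freedom. No patients, visits or data are added, since baseline FACIT-F is already scheduled in Table 3.
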